#### 2.2.2. Secondary Endpoints

- Efficacy assessed as:
  - HBsAg responder rate (decrease from baseline  $\geq 1.0$  on the  $\log_{10}$  scale) at Week 16 of treatment and Weeks 20, 28 and 40 of follow up.
  - HBsAg responder rate (decrease from baseline  $\geq 0.5$  on the  $\log_{10}$  scale) at Weeks 12 and 16 of treatment and Weeks 20, 28 and 40 of follow up.
  - HBsAg loss rate (% patients with HBsAg < LLOQ) at Week 16 of treatment and Weeks 20, 28 and 40 of follow-up.
  - HBsAg loss rate (Proportion of results that are Target Not Detected versus Target Detected) at Week 16 of treatment and Weeks 20, 28 and 40 of follow-up
  - Relapse rate HBsAg (% patients who became negative [HBsAg < LLOQ], then increased with HBsAg > LLOQ) at Week 16 of treatment period and Weeks 20, 28 and 40 during follow-up period

---

 Breakthrough is defined by quantifiable HBV DNA increase of  $\geq 1 \log_{10}$  HBV DNA copies/mL above LLOQ. Breakthrough samples will be further assessed for resistance assessments, including both for the nucleos(t)ide analogue as well as for EYP001a (e.g., sequence analysis of FXR response elements in HBV genome). Details will be described in the Laboratory manual. Also refer footnote no. 9 below.

- Virologic failure rate (breakthrough) of HBV-DNA (% patients with a confirmed quantifiable HBV DNA increase of  $\geq 1\log_{10}$  HBV DNA copies/mL above LLOQ) assessed at Week 16 of treatment period and Weeks 20, 28 and 40 during follow-up period
- HBV-pgRNA decline ( $\Delta \log_{10}$ ) from Day 1 to Weeks 4, 8, 12, 16 of treatment period and Week 40 of maintenance period
- HBcrAg decline ( $\Delta \log_{10}$ ) from Day 1 to Weeks 4, 8, 12, 16 of treatment period and Week 40 of maintenance period
- HBeAg quantification for HBeAg pos patients and changes at Week 16 of treatment and Week 40 of follow-up
- Fibroscan VCTE change from screening value to Weeks 16 and 40 or ET value
  
- Safety and Tolerability assessed as:
  - Treatment-emergent adverse events (TEAEs) (including SAEs)
  - All-cause mortality
  - Clinical laboratory tests
  - Pruritus assessment
  - Vital signs (blood pressure, heart rate, respiratory rate, and temperature)
  - Concomitant medications
  - Physical examinations
  - 12-lead ECG
  
- PK assessed as:
  - Plasma concentration of EYP001a or any relevant active metabolites (as identified in an ongoing phase 1 study)
  
- PD biomarkers:

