### Secondary efficacy variables

The secondary efficacy variables are as follows:

- HBsAg responder rate (decrease from baseline  $\geq 1.0$  on the  $\log_{10}$  scale) at Week 16 of treatment and Weeks 20, 28 and 40 of follow up.
- HBsAg responder rate (decrease from baseline  $\geq 0.5$  on the  $\log_{10}$  scale) at Weeks 12 and 16 of treatment and Weeks 20, 28 and 40 of follow up.
- HBsAg loss rate (% patients with HBsAg < LLOQ) at Weeks 16 of treatment period and Weeks 20, 28 and 40 of follow-up.
- HBsAg loss rate (proportion of results that are Target Not Detected versus Target Detected) at Weeks 16 of treatment period and Weeks 20, 28 and 40 of follow-up.
- relapse rate HBsAg (% patients who became negative [HBsAg < LLOQ], then increased with HBsAg > LLOQ) at Week 16 of treatment period and Weeks 20, 28 and 40 during follow-up period.
- Virologic failure rate (breakthrough) of HBV DNA (% patients with a confirmed quantifiable HBV DNA increase of  $\geq 1 \log_{10}$  HBV DNA copies/mL above LLOQ) assessed at Week 16 of treatment period and Weeks 20, 28 and 40 during follow-up period
- HBV pgRNA decline ( $\Delta \log_{10}$ ) from Day 1 to Weeks 4, 8, 12 and 16 of treatment period and Week 40 of maintenance period
- HBcrAg decline ( $\Delta \log_{10}$ ) from Day 1 to Weeks 4, 8, 12 and 16 of treatment period and Week 40 of maintenance period
- HBeAg quantification for HBeAg pos patients and changes at Week 16 of treatment and Week 40 of follow-up
- Fibroscan VCTE change from screening to Weeks 16 and 40 or ET

Analysis of HBV response markers:

- Samples for analysis of quantitative HBsAg and quantitative HBV-DNA will be collected at pre-dose on all study visits during treatment period and Weeks 20, 28 and 40 of follow-up or at the ET visit.
- Samples for analysis of quantitative HBV pgRNA and HBcrAg will be collected at pre-dose on all study visits during treatment period and Week 40 of maintenance during follow-up period or at the ET visit.

---

 Breakthrough samples will be further assessed for resistance assessments, including both for the nucleos(t)ide analogue as well as for EYP001a (e.g., sequence analysis of FXR response elements in HBV genome). Details will be described in the Laboratory manual.

 HBV DNA results <LLOQ will be reported as either <LLOQ/Detected (i.e. LLOQ/TD) or <LLOQ/Target Not Detected (i.e. LLOQ/TND), both are considered LLOQ.

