#### *11.3.3.2. Secondary Efficacy*

HBsAg responder rate (decrease from baseline  $\geq 1.0$  on the  $\log_{10}$  scale and decrease from baseline  $\geq 0.5$  on the  $\log_{10}$  scale) and HBsAg loss rate (proportion of HBsAg < LLOQ) at Week 16 of treatment and Week 20, Week 28 and Week 40 of follow-up will be analysed as key secondary endpoints at 16 weeks, and 40 weeks. Proportion of patients of Target not detected will be analysed as exploratory endpoint. HBsAg responder rate (decrease from baseline  $\geq 0.5$  on the  $\log_{10}$  scale) will also be analysed at Week 12 of treatment. At 16 and 40 weeks, these endpoints will be analysed taking into account multiplicity by a combination of a hierarchical fixed test procedure and a Hochberg procedure (See [Section 11.4.2](#)), using a this Pearson Chi-square test. At other timepoints, analyses for these two endpoints will be descriptive.

Relapse rate HBsAg (% patients who became negative [HBsAg < LLOQ], then increased with HBsAg > LLOQ) at Week 16 of treatment period and Weeks 20, 28 and 40 during the follow-up period will be summarized by frequency counts and percentages.

Virologic failure rate (breakthrough) of HBV DNA (% patients with a confirmed quantifiable HBV DNA increase of  $\geq 1\log_{10}$  HBV DNA copies/mL above LLOQ) assessed at Weeks 16 of treatment, 20, 28 and 40 during follow up period will be summarized by frequency counts and percentages.

HBV-pgRNA decline ( $\Delta \log_{10}$ ) and HBcrAg decline ( $\Delta \log_{10}$ ) from Day 1 to Weeks 4, 8, 12 and 16 of the treatment period and Week 40 of maintenance period, HBeAg quantification for HBeAg positive patients and changes at Week 16 of treatment and Week 40 of follow-up and Fibroscan VCTE change from screening value to the Weeks 16 and 40 or ET visit will be summarized through descriptive statistics.

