### 11.4.2. Testing strategy and power for key secondary endpoints

Multiplicity is taken into account by using a combination of a hierarchical fixed test procedure and a Hochberg procedure.

Only in case the primary endpoint is significant at 16 weeks, the key secondary endpoint “HBsAg loss rate” will be tested at the same one-sided  $\alpha$  level of 0.05, using a Hochberg procedure. This procedure goes as follows: the p-values will be ordered from small to large

$p_{(1)} \leq p_{(2)}$ . largest p-value  $p_{(2)}$  will be compared to  $\alpha=0.05$ . If significant, then both hypotheses will be rejected. If not, the smallest p-value is compared to  $\alpha/2=0.025$ . If significant, then only the hypothesis corresponding to the smallest p-value is rejected.

At 40 weeks, the key secondary endpoints HBsAg responder rate and HBsAg loss rate will be tested a one-sided  $\alpha$  level of 0.05, using a Hochberg procedure.

To calculate the power to detect a difference in HBsAg loss rate, we assumed a proportion of 0.5% in the placebo arm, and of 10% in the experimental arm. A trial including 49 patients results in a power of about 55% for this endpoint (using an un-pooled estimate of the variance), using a one-sided  $\alpha$  of 0.05.

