Please note that for this study, first study drug dosing is considered to occur on Day 1.

- **Breakthrough:** Quantifiable HBV DNA increase of $\geq 1 \log_{10}$ HBV DNA copies/mL above LLOQ.
- **Lower limit of quantification (LLOQ):** HBV DNA results i.e HBsAg < LLOQ will be reported as either <LLOQ/Detected (i.e. LLOQ/TD) or <LLOQ/Target Not Detected (i.e. LLOQ/TND), both are considered LLOQ. HBsAg loss rates will be further subdivided accordingly.

- HBsAg decline: Change from Baseline in HBsAg on the log₁₀ scale. Negative values indicate a decline.
- HBsAg loss: Patients with HBsAg < LLOQ/TND.
- HBsAg responder A: A decrease from baseline ≥ 1.0 on the log₁₀ scale, i.e. a change from baseline of ≤ -1.0 . HBsAg results <LLOQ/Target Not Detected will be reported as 0.015 [$\log_{10}(0.015) = -1.852$] and HBsAg < LLOQ/Target Detected will be reported as midpoint between LLOQ/Target Not Detected and LLOQ/Target Detected, i.e. 0.04IU/mL = $\log_{10}(0.04) = -1.4$. Also, HBsAg above LLOQ will be reported as the raw data is reported.
- HBsAg responder B: A decrease from baseline ≥ 0.5 on the log₁₀ scale, i.e. a change from baseline of ≤ -0.5 . HBsAg results <LLOQ/Target Not Detected will be reported as 0.015 [$\log_{10}(0.015) = -1.852$] and HBsAg < LLOQ/Target Detected will be reported as midpoint between LLOQ/Target Not Detected and LLOQ/Target Detected, i.e. 0.04IU/mL = $\log_{10}(0.04) = -1.4$. Also, HBsAg above LLOQ will be reported as the raw data is reported.
- HBsAg Relapse Rate: Patients who became negative (HBsAg<LLOQ), then increased with HBsAg > LLOQ. HBsAg results <LLOQ/Target Not Detected will be reported as 0.015 [$\log_{10}(0.015) = -1.852$] and HBsAg < LLOQ/Target Detected will be reported as midpoint between LLOQ/Target Not Detected and LLOQ/Target Detected, i.e. 0.04IU/mL = $\log_{10}(0.04) = -1.4$. Also, HBsAg above LLOQ will be reported as the raw data is reported.
- Virologic failure: Patients with a confirmed quantifiable HBV DNA increase of $\geq 1 \log_{10}$ HBV DNA copies/mL above LLOQ. HBV DNA results < LLOQ/Target Not Detected will be reported as 10 [$\log_{10}(10) = 1$] and HBV DNA < LLOQ/Target Detected will be reported as midpoint between LLOQ/Target Not Detected and LLOQ/Target Detected, i.e. 20IU/mL = $\log_{10}(20) = 1.3$. Also, HBV DNA above LLOQ will be reported as the raw data is reported.
- HBV-pgRNA decline: Change from Baseline in HBV-pgRNA on the log₁₀ scale. Negative values indicate a decline.

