- HBsAg responder rate (decrease from baseline ≥ 0.5 on the \log_{10} scale) at 16 of treatment and Weeks 40 of follow up.
 - Hypothesis: H_0 : Treatment is not associated with endpoint
 H_A : Treatment is associated with endpoint
 - Time Points: Week 16 and Week40.
 - The Pearson Chi-squared test will be used to compare the differences in proportions between the treatment groups at Week 16 and Week 40. At Week 16 and Week 40, this endpoint will consider multiplicity considering multiplicity by a combination of a hierarchical fixed test procedure and a Hochberg procedure (see section 3.4 for more detail). The analysis will be based on a one-sided test at a 5% level of significance.
- HBsAg loss rate (% patients with HBsAg < Lower Limit of Quantification (LLOQ)/TND) at Week 16 of treatment and Week 40 of follow-up.
 - Hypothesis: H_0 : Treatment is not associated with endpoint
 H_A : Treatment is associated with endpoint
 - Time Points: Week 16 and Week40.
 - The Pearson Chi-squared test will be used to compare the differences in proportions between the treatment groups at Week 16, and Week 40. At Week 16 and Week 40, this endpoint will consider multiplicity by a combination of a hierarchical fixed test procedure and a Hochberg procedure (see section 3.4 for more detail). The analysis will be based on a one-sided test at a 5% level of significance.
- HBsAg loss rate (% patients with HBsAg < Lower Limit of Quantification (LLOQ)/TD) at Week 16 of treatment and Week 40 of follow-up.
 - Hypothesis: H_0 : Treatment is not associated with endpoint
 H_A : Treatment is associated with endpoint
 - Time Points: Week 16 and Week 40.

- The Pearson Chi-squared test will be used to compare the differences in proportions between the treatment groups at Week 16, and Week 40. At Week 16 and Week 40, this endpoint will consider multiplicity by a combination of a hierarchical fixed test procedure and a Hochberg procedure (see section 3.4 for more detail). The analysis will be based on a one-sided test at a 5% level of significance.

3.4 Multiple Comparisons and Multiplicity Adjustments.

For the analysis of secondary endpoints during the final analysis, multiplicity will be considered by using a combination of a hierarchical fixed test procedure and a Hochberg procedure.

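### The SAP narrows HBsAg loss from <LLOQ to <LLOQ/TND, does not say whether its second loss test (<LLOQ/TD) counts TND patients, and lists neither this nor the four-test Week 16 family in Section 15

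*SAP*

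**What the plan says.** **Protocol.** Section 11.3.3.2 gives the key secondary as "HBsAg loss rate (proportion of HBsAg < LLOQ) at Week 16 of treatment" (and later weeks), with formal testing at Weeks 16 and 40. It adds: "Proportion of patients of Target not detected will be analysed as exploratory endpoint". The protocol is not wholly consistent, because Section 2.2.2 also lists among the secondary endpoints "HBsAg loss rate (Proportion of results that are Target Not Detected versus Target Detected"; the synopsis and Section 7.1 do the same. Only 11.3.3.2 assigns an analysis status to TND.

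**SAP definition.** Section 3.2 states "HBsAg loss: Patients with HBsAg < LLOQ/TND". It also describes results below LLOQ as falling into a TD or a TND category, says both count as LLOQ, and adds "HBsAg loss rates will be further subdivided accordingly".

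**SAP tests.** Sections 3.3, 3.4 and 12.1 test two loss rates formally: <LLOQ/TND (Loss A, Table 14.2.3.1) and "HBsAg loss rate (% patients with HBsAg < Lower Limit of Quantification (LLOQ)/TD) at Week 16 of treatment and Week 40 of follow-up" (Loss B, Table 14.2.3.2).

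**Week 16 family.** Protocol 11.4.2 names only loss at Week 16 but orders two p-values: "If significant, then both hypotheses will be rejected". Protocol 11.3.3.2 puts three rates under the same procedure: responder at 1.0 log, responder at 0.5 log, and loss. SAP 3.4 orders four p-values: two loss rates and two responder rates.

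**SAP Section 15.** Its table of changes covers imputation, fibrosis inference, CTCAE maxima, anti-HBs and anti-HBe, and genotype. It does not mention the loss definition or the Hochberg family.

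**The concern.** The issue is which endpoint is tested, not power. A programmer who follows SAP 3.2 reports a key secondary loss rate that is not the protocol's. A programmer who builds Loss B has to choose between TD only and TD plus TND, and nothing in either document settles it. On the TD-only choice, a patient with the deepest response (TND) counts as a non-event on Loss B. Two competent programmers could therefore report different key secondary rates from the same data.

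Timing matters because SAP 16.1 unblinds all patients after the Week 16 database lock. A reading chosen after that point could be seen as driven by the data.

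**Working it through.** **Inputs.** One-sided alpha is 0.05 (SAP 3.3 and 3.4). Assumed loss rates are 0.5% on placebo and 10% on EYP001a (Protocol 11.4.2; SAP 2.4 and 3.4). Allocation is 37:12 (SAP 2.5). The test is Pearson chi-squared (SAP 3.3). The documents do not give three things assumed here: the TND share of results below LLOQ, zero control events in the illustrations, and a 19:6 split of the roughly 25 patients randomized when enrolment was suspended (SAP 15).

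**1. The plan's own figure.** Un-pooled power = Φ((p1 − p0)/SE − 1.645), with SE = √(0.10×0.90/37 + 0.005×0.995/12) = 0.0534. This gives Φ(0.095/0.0534 − 1.645) = 55.4%, matching the stated 55%. That figure belongs to a single loss endpoint tested at the full 0.05.

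**2. The two readings of Loss B.**
- *TD only.* SAP 3.2 presents TD and TND as alternatives and subdivides the loss rates accordingly. Then Loss A is TND, Loss B is TD without TND, and the protocol's <LLOQ rate is tested nowhere.
- *TD plus TND.* SAP 3.2 imputes a TD result at the midpoint between the two labels, which treats LLOQ/TD as an upper limit. The footnote to Table 14.2.3.2 likewise describes Loss B as a value below LLOQ/TD. Then Loss B is the protocol endpoint, and Loss A is the TND analysis promoted from exploratory to formal.

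Both readings depart from Protocol 11.3.3.2.

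**3. Size on one data set.** Take x/37 against 0/12, with pooled rate p̄ = x/49 and z = (x/37)/√(p̄(1−p̄)(1/37 + 1/12)).
- Eight below LLOQ, four of them TND: the protocol rate is 8/37 = 21.6%, one-sided p = 0.039. Loss under SAP 3.2 is 4/37 = 10.8%, p = 0.117. Loss B is 8/37 if it includes TND and 4/37 if it does not.
- With the TND share at 25%, 50% or 75% of those eight, loss under SAP 3.2 is 2/37, 4/37 or 6/37 (5.4%, 10.8%, 16.2%).
- Eight is the smallest count that crosses 0.05 with no control event. At the planned rate, 0.10×37 = 3.7, about four patients. The composite then gives 4/37, p = 0.117, and a TND half gives 2/37, p = 0.205. Neither is significant.

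**4. Family size.** The last Hochberg step is 0.05/2 = 0.025, 0.05/3 = 0.0167 or 0.05/4 = 0.0125. With no control events, loss passes that step at 10, 11 or 12 of 37, or at 9, 10 or 10 of 19. More hypotheses make the last step stricter.

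**5. Power under the planned test.** Exact enumeration of the one-sided Pearson test at 0.05, for 10% against 0.5%, gives 2.6% at 37:12 and 0.2% at 19:6. Correcting the definition does not change this.

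**The case against.** A reader might infer that <LLOQ/TD is undefined. That goes too far: SAP 3.2 describes it as a result category, SAP 3.5 gives it an imputation rule, and Table 14.2.3.2 footnotes Loss B. What is missing is narrower, namely whether TND counts in Loss B.

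A reader might also infer that the protocol's endpoint has been dropped. That follows only on the TD-only reading.

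A third inference is that the family simply doubled from two to four. Protocol 11.4.2 orders two p-values while naming one Week 16 endpoint, and Protocol 11.3.3.2 already names three rates. Four exceeds either count, but the protocol offers no single baseline. Nor does the larger family inflate error, since it is stricter.

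It can also be said that the 8/37 illustration sits at the tipping point and at more than twice the planned rate, that 37:12 is unlikely with enrolment suspended near 25, and that a changed test conclusion is improbable. All of that stands. So does the point that keeping both tests, defining Loss B and recording the change would also remove the ambiguity, given that the protocol lists TND versus TD among its secondaries elsewhere. None of this supplies the missing definition or the missing Section 15 entries.

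**Conclusion.** The point holds as a definition and documentation fault that should be fixed. SAP 3.2 defines key secondary loss more narrowly than Protocol 11.3.3.2, Loss B admits two readings, the Week 16 family is larger than either protocol count, and Section 15 lists none of this. In the illustration the reported loss rate is 21.6% or 10.8% depending on the definition; that gap rests on the assumed half-TND share.

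The documents do not support calling this an error-rate problem, or claiming that a correction would rescue power. The stakes are limited: these are low-power secondaries in an exploratory Phase 2a trial, tested at Week 16 only if the primary succeeds, and at the planned 10% rate neither definition would be significant.

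**What to change.** Before the Week 16 lock and unblinding:

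- Define HBsAg loss throughout the SAP (2.3.2, 3.2, 3.3, 3.4, 12, 12.1) and in Tables 14.2.3.x as HBsAg <LLOQ, whether TD or TND. Test it once at Week 16 and once at Week 40.
- Report TND alone, and the TD/TND split, descriptively as exploratory, in line with Protocol 11.3.3.2.
- State the Hochberg family at each week. With loss, responder A and responder B, the steps are 0.05, 0.025 and 0.0167. The Week 40 sentence in SAP 3.4 names a single loss rate while 3.3 tests two, so the two sections need aligning.
- Add Section 15 rows for the loss definition and for the Week 16 family. The second row should note that Protocol 11.3.3.2 (three rates) and 11.4.2 (two p-values) disagree, and say which one the SAP follows.

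The cost is wording in the SAP and table shells plus the Section 15 rows; no new data are needed. The downside is that TND alone loses its formal test.

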3.3 Inferential Analyses

Descriptive statistics will be used to summarize the safety and PK data. No formal hypothesis testing is planned. All efficacy analyses (unless otherwise specified) will be performed at a one-sided 5% level of significance.

- HBsAg decline ($\Delta \log_{10}$) from Day 1 to Week 16 of treatment (primary)
 - Hypothesis:
 - H₀₁: Adjusted Mean for experimental arm at Week xx minus Adjusted Mean for control arm at Week xx = 0, where xx = 2, 4, 6, 8, 10, 12, 14, and 16
 - H₁₁: Adjusted Mean for experimental arm at Week xx minus Adjusted Mean for control arm at Week xx = -1, where xx = 2, 4, 6, 8, 10, 12, 14, and 16.

- Time Points: Change from baseline until to Week 16 of treatment.
 - A general linear model for repeated measures will be used to assess HBsAg decline ($\Delta \log_{10}$), using the stratification factors as independent variables in the model (HBeAg pos [yes, no]). Baseline HBsAg level will be included as a covariate. The analysis will be based on a one-sided test at a 5% level of significance. Degrees of freedom calculation will be based on the Kenward-Roger method. The unstructured covariance matrix structure to model the within-patient errors will be selected initially. If the unstructured covariance structure leads to non-convergence, covariance matrix structure will be selected through the maximum likelihood method. The final model will then we rerun by using the reduced maximum likelihood method.
- The following covariates will be included for this model:
- i. Baseline HBsAg level
 - ii. HBeAg positive [yes, no]
 - iii. Treatment Group
 - iv. Study visit
 - v. Interaction between treatment group and study visit
- The least-squares mean change from baseline, along with corresponding 95% CI and SE for treatment arms and experimental arm versus control arm at the one-sided 0.05 level will be provided for Week 2, 4, 6, 8, 10, 12, 14 and 16 for the ITT population (with Multiple imputation). This will be repeated for ITT (with no imputation), mITT (with Multiple imputation), mITT (with no imputation), PP set (with Multiple imputation) and PP set (no imputation).
 - If applicable, this model will be re-analyzed with the genotype covariate as “sensitivity analysis”.
- Liver Fibrosis and inflammation change from baseline from Day 1 to Week 16 of treatment
 - Hypothesis:

H_0 : Adjusted Mean for experimental arm at Week xx minus Adjusted Mean for control arm at Week xx = 0, where xx = 4, 8, 12 and 16

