H_1 : Adjusted Mean for experimental arm at Week xx minus Adjusted Mean for control arm at Week xx \neq 0, where xx = 4, 8, 12 and 16.
 - Time Points: Change from baseline until to Week 16 of treatment.
 - A general linear model for repeated measures will be used to assess Liver Fibrosis and inflammation parameters including ALT, AST, AST/ALT ratio, high sensitivity C-reactive protein, interleukin 6, tumour necrosis factor alpha, procollagen type III N terminal peptide (Pro C3), tissue inhibitor of metalloproteinases-1, using the stratification factors as independent variables in the model (HBeAg pos [yes, no]). Baseline Liver Fibrosis and inflammation parameters value will be included as a covariate. The analysis will be based on a two-sided test at a 5% level of significance. Degrees of freedom calculation will be based on the Kenward-Roger method. The unstructured covariance matrix structure will be selected initially. If the unstructured covariance structure leads to non-convergence, covariance matrix structure will be selected through the maximum likelihood method. The final model will then we rerun by using the reduced maximum likelihood method.

The following covariates will be included for this model:

 - i. Baseline liver fibrosis and inflammation parameters value
 - ii. HBeAg positive [yes, no]
 - iii. Treatment Group

- iv. Study visit
 - v. Interaction between treatment group and study visit
- The least-squares mean change from baseline, along with corresponding 95% CI and SE for treatment arms and experimental arm versus control arm at the two-sided 0.05 level will be provided for Week 4, 8, 12 and 16 for the Safety Set.
- If applicable, this model will be re-analyzed with the genotype covariate as “sensitivity analysis”.
- HBsAg responder rate (decrease from baseline ≥ 1.0 on the \log_{10} scale) at Week 16 of treatment and Weeks 40 of follow up. (secondary)
 - Hypothesis: H_0 : Treatment is not associated with endpoint
 H_A : Treatment is associated with endpoint
 - Time Points: Week 16 and Week 40.
 - The Pearson Chi-squared test will be used to compare the differences in proportions between the treatment groups at Week 16 and Week 40. At Week 16 and Week 40, this endpoint will consider multiplicity by a combination of a hierarchical fixed test procedure and a Hochberg procedure (see section 3.4 for more detail). The analysis will be based on a one-sided test at a 5% level of significance.

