Only if the primary endpoint is significant at 16 weeks, the key secondary endpoints “HBsAg loss rate (<LLOQ/TND and <LLOQ/TD)” and “HBsAg responder rates (B and A see section 3.2)” will be tested at the same one-sided α level of 0.05, using a Hochberg procedure at Week 16. This procedure goes as follows: the p-values will be ordered from small to large $p(1) \leq p(2) \leq p(3) \leq p(4)$. The largest p-value $p(4)$ will then be compared to $\alpha=0.05$. If significant, then all hypotheses will be rejected. If not, the next largest p-value $p(3)$ is compared to $\alpha/2=0.025$. If significant, then these hypotheses corresponding to $p(1)$, $p(2)$ and $p(3)$ are rejected. If not, the next largest p-value $p(2)$ is compared to $\alpha/3=0.017$. If significant, then both hypotheses corresponding to $p(1)$ and $p(2)$ are rejected. If not, the smallest p-value is compared to $\alpha/4=0.0125$. If significant, then only the hypothesis corresponding to the smallest p-value is rejected.

At 40 weeks, the key secondary endpoints HBsAg responder rates (B and A) and HBsAg loss rate will be tested a one-sided α level of 0.05, using a Hochberg procedure.

To calculate the power to detect a difference in HBsAg loss rate, we assumed a proportion of 0.5% in the placebo arm, and of 10% in the experimental arm. A trial including 49 patients results in a power of about 55% for this endpoint (using an un-pooled estimate of the variance), using a one-sided α of 0.05.

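### The plan describes a hierarchical procedure for the Week 40 key secondary tests, but the rule as written has no such step and gives Week 40 a separate, unconditional one-sided 5%

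*SAP*

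**What the plan says.** **Description of the strategy.** For the responder and loss endpoints, SAP 3.3 says: "At Week 16 and Week 40, this endpoint will consider multiplicity by a combination of a hierarchical fixed test procedure and a Hochberg procedure", and refers to SAP 3.4 for detail. Protocol 11.3.3.2 describes the same combination at 16 and 40 weeks.

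**Rule for Week 16.** SAP 3.4 opens this family with a gate: "Only if the primary endpoint is significant at 16 weeks". Four hypotheses (loss by TND, loss by TD, responder A, responder B) then "will be tested at the same one-sided α level of 0.05, using a Hochberg procedure at Week 16", with thresholds 0.05, 0.025, 0.017 and 0.0125.

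**Rule for Week 40.** The next paragraph of SAP 3.4 reads "At 40 weeks, the key secondary endpoints HBsAg responder rates (B and A) and HBsAg loss rate will be tested" and completes the rule with "will be tested a one-sided α level of 0.05, using a Hochberg procedure". It attaches no condition on the primary or on Week 16, and it does not share alpha with Week 16. Protocol 11.4.2 is built the same way: "At 40 weeks, the key secondary endpoints HBsAg responder rate and HBsAg loss rate will be tested a one-sided" level of 0.05, again by Hochberg and without a condition.

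**Primary.** SAP 3.3: "The analysis will be based on a one-sided test at a 5% level of significance".

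The table of changes in SAP 15 adds no Week 40 gate. Neither document gives a numerical overall error rate.

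**The concern.** The description and the rule do not match. SAP 3.3 promises a hierarchy at Week 40, yet the section it points to has a hierarchical step for Week 16 only. A programmer working from SAP 3.4 would run the Week 40 Hochberg procedure whatever the primary showed, and could report a formal rejection, labelled as multiplicity-controlled, after the primary had failed. A hierarchy exists to prevent that outcome.

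The Week 40 family is also not fully defined. Week 16 names loss by TND and by TD, whereas Week 40 names only the loss rate. The family therefore has three or four members, and its smallest Hochberg threshold is 0.05/3 = 0.0167 or 0.05/4 = 0.0125.

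**Working it through.** **1. The plan's own figures reproduce.**
- Loss-rate power (0.5% v 10%, 12 v 37 patients, un-pooled variance, one-sided 0.05): SE = √(0.10×0.90/37 + 0.005×0.995/12) = 0.0534. Then 0.095/0.0534 = 1.78, and power = Φ(1.78 − 1.645) = 55.4%. The SAP states about 55%.
- Primary (effect 0.9, SD 1.08, 3:1, one-sided 0.05, N = 49): the t-test gives 80.1% power at exact 3:1 and 79.6% at 37:12. The plan states 80%.

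**2. Ceiling on the error as written.** Take all nulls as true. The Week 16 family adds nothing, because it opens only after the primary has been rejected. Two 5% opportunities remain, the primary and Week 40.
- Independent: 1 − 0.95² = 9.75%.
- Any dependence (Bonferroni bound, with Hochberg holding its level within the family): 0.05 + 0.05 = 10%.

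**3. Correlated normal statistics.** Monte Carlo with one primary and three or four Week 40 statistics gave 6.1% to 9.7%. The rate falls as correlation rises.

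**4. The planned tests.** This simulation used a Week 16 t-test and one-sided Pearson chi-square tests at Week 40 on three nested endpoints, 37:12, all nulls true. Null event rates, correlations and normality are assumptions, because the documents do not give them.

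| Assumption | False claim, primary or Week 40 |
|---|---|
| SD of change 1.08 (plan's value), Week 16–40 correlation 0 to 0.8 | about 6.0–6.7% |
| SD 0.5 | 5.1–5.2% |
| SD 0.3 | about 5%, no Week 40 rejections |
| Null rates 32/18/1%, 50/30/5% or 50/30/20% | 6.4–7.7% |
| Null rates 60/40/30% | 7.7–8.4% |
| All three rates 40% | 9.1–10.0% (upper value within simulation error of 9.75%) |

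At SD 1.08 the Week 40 family alone rejects in roughly 1.5 to 1.8% of trials, well below its nominal 5%. With 12 controls and uncommon events the chi-square test is conservative.

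**5. Which gates control the error.** Normal statistics, over a range of correlations:

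| Rule for Week 40 | Setting | False secondary claim |
|---|---|---|
| Primary significant, full 0.05 in each family | Primary real, all secondary nulls true | 5.3–9.6% |
| Primary plus at least one Week 16 rejection, full 0.05 in each | Primary and one Week 16 effect real | up to 9.6% |
| Primary plus all Week 16 hypotheses rejected | Same as the row above | 3.7–5.0% |
| Primary significant, 0.025 per family | Same as the row above | 3.1–4.9% |

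The first two rules leak because, once open, Week 16 and Week 40 each spend a full 5%.

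**The case against.** **It may be an omitted sentence.** The documents say three times over (SAP 3.3, the opening of SAP 3.4, protocol 11.3.3.2) that hierarchy and Hochberg are combined, and the only hierarchical step written is the primary gate. A fair reading is that the gate was meant to govern both paragraphs. That stands as a reading of intent, and a reader who infers a deliberate second 5% goes further than the text allows. It does not rescue the rule, which still has to be written out. Repeating the primary gate alone would also leave two full 5% families behind it.

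**No overall 5% is promised.** A reader might infer that the trial breaks a stated 5% overall error rate. The documents do not support this: their 5% figures attach to single tests or to a family. What fails is the multiplicity procedure the plan describes.

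**A 10% error is not the expected value.** A reader might also infer that the error is about 10%. That needs near-independent statistics and tests that use their full level. Protocol Table 1 shows 4-week HBsAg SDs of about 0.1 to 0.2, which point to few null responders, although 16-week values could differ. SAP 15 records enrolment suspended after about 25 randomizations. At an assumed 19:6 and SD 1.08 the error is 5.2–5.5%. This objection stands.

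**The trial is exploratory.** Protocol 5.4 calls it an early Phase 2a exploratory study, and separate families by time point are a recognised choice there. That lowers the stakes, but a plan making that choice should say so and not describe a hierarchy.

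**Conclusion.** The point holds as an inconsistency between the described strategy and the operative rule. As written, a formal Week 40 claim is possible after a failed primary. The chance of a false claim on the primary or at Week 40 cannot exceed about 9.75–10%. For the planned 37:12 chi-square tests it is more plausibly 5–8%, and close to 5% if responders are rare. The ceiling follows from the stated alphas. The lower range rests on assumed null event rates, correlations and normal changes. The undefined membership of the Week 40 family is a separate gap that leaves its Hochberg thresholds open. This should be corrected because it is cheap and affects how Week 40 results may be labelled. It does not put the primary analysis in doubt.

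**What to change.** Amend SAP 3.4 to test the Week 40 family only if the primary is significant and one of these applies:

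- **(a)** every Week 16 key secondary hypothesis has been rejected, in which case Week 40 uses one-sided 0.05; or
- **(b)** the one-sided 0.05 is split in advance, 0.025 to Week 16 and 0.025 to Week 40.

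State that Week 40 p-values are otherwise nominal. List the Week 40 hypotheses, saying whether loss means TND, TD or both, and give the resulting thresholds. Align SAP 3.3 and the notes to mock tables 14.2.3.1 to 14.2.4.2, and record the change from protocol 11.4.2 in SAP 15. Date the amendment before the additional Week 16 database lock in SAP 16.1, since all patients are unblinded after it.

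**Cost.** A few sentences, and no formal Week 40 claim when the gate is not met. Option (a) is demanding: rejecting all four Week 16 hypotheses requires the loss tests to reach 0.05, and the plan's own power for loss is about 55%, so on those assumptions Week 40 would open at most about that often. Option (b) lowers the alpha per family. For a single loss test at 0.025 the same calculation gives Φ(1.78 − 1.96), about 43%, in place of 55%.
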